Cytochrome P450 (CYP) 2D6 IM, EM and URM patients will be treated with eliglustat 84 mg twice daily (BID). Cytochrome P450 (CYP) 2D6 PM patients will be treated with eliglustat 84 mg once daily (QD). Doses may have to be decreased when certain concomitant medications are administered (see [Section 8.5.1.2](#)).

Eliglustat tartrate (the drug substance) is an L tartaric acid salt, and exists in plasma as a free base, Genz-99067, which is the active moiety. Throughout this document, Genz-99067 is used when referring to drug exposure (eg, plasma concentrations), and eliglustat is used in all other instances with doses reflecting the tartrate form.

5 STUDY OBJECTIVES

5.1 PRIMARY

To evaluate the long term skeletal response to eliglustat in adult patients who successfully completed one of the Phase 2 or Phase 3 studies of eliglustat.

5.2 SECONDARY

The secondary objectives are to evaluate:

- The safety of eliglustat by (S)AE continuous monitoring,
- The quality of life by Short Form-36 Health Survey and
- Biomarkers of GD1 (chitotriosidase, plasma GL-1 and lyso-GL-1).

6 STUDY DESIGN

6.1 DESCRIPTION OF THE PROTOCOL

This is an open label, interventional, non-comparative, multicenter, multinational Phase 3b study to evaluate long term skeletal responses to eliglustat, eliglustat safety and effect on quality of life in adult patients who successfully completed one of the Phase 2 or Phase 3 studies in the eliglustat program. This study is considered an extension of these previous studies with the goal of obtaining longer term data.

6.2 DURATION OF STUDY PARTICIPATION

6.2.1 Duration of study participation for each patient

The duration of study participation for individual patients will be at least 2 years (unless early discontinuation occurs) and up to 4 years, or until commercial eliglustat is available to patients through reimbursement. If after 4 years since the beginning of the study eliglustat is not approved and available to patients in participating country, patients in this country may continue to receive study treatment until eliglustat is available to patients through the compassionate use (expanded access) program or is approved and available through reimbursement, whichever comes first.

The study will include

- A screening period that can extend from Day -45 to Day-1,
- A long-term treatment period up to 4 years or until eliglustat is available to patients through reimbursement or through the compassionate use (expanded access) program, starting on Day 1

After study completion, patients will be encouraged to enroll in the ICGG Gaucher Registry.

6.2.2 Determination of end of clinical trial (all patients)

The end of the study is defined as the last visit for the last patient.

6.3 INTERIM ANALYSIS

No interim analysis is planned.

6.4 STUDY COMMITTEES

The study data will not be reviewed by a Data Monitoring Committee. The IMP is approved for the treatment of Gaucher disease type 1 patients, the study population, by the FDA, EMA and

TGA. This is an extension study for patients who have been receiving the IMP for 4-8 years prior to enrollment in the study.

7 SELECTION OF PATIENTS

The patients who have completed successfully the Phase 2 study (GZGD00304) or one of the Phase 3 studies (GZGD02507, GZGD02607 or GZGD03109) in the eliglustat program will be invited to participate in this study.

7.1 INCLUSION CRITERIA

I 01. The patient must have successfully* completed the Phase 2 (GZGD00304) or a Phase 3 study (GZGD02507, GZGD02607 or GZGD03109).

* Successful completion is defined as patients enrolled in one of the above mentioned studies who received eliglustat through the end of the study and completed the end of study (EOS) visit without having discontinued or being withdrawn prematurely.

I 02. The patient is willing and able to provide signed informed consent prior to any protocol required procedures being performed.

I 03. Female patients of childbearing potential must have a documented negative pregnancy test prior to enrollment and while they are receiving eliglustat treatment

I 04. Female patients of childbearing potential must be willing to practice true abstinence in line with their preferred and usual lifestyle, or use a medically accepted form of contraception (either a barrier method, such as condom or diaphragm + spermicide, or a non-barrier method such as oral, injected, or implanted hormonal methods, or an intra-uterine device or system) while receiving eliglustat.

7.2 EXCLUSION CRITERIA

Patients who have met all the inclusion criteria listed in [Section 7.1](#) will be screened for the following exclusion criteria that are sorted and numbered in the following 4 subsections:

7.2.1 Exclusion criteria related to study methodology

E 01. The patient is unwilling to comply with the requirements of the protocol.

E 02. The patient has received an investigational product (other than eliglustat) within 30 days prior to enrollment.

E 03. The patient has received miglustat within the 6 months prior to enrollment.

E 04. The patient has documented prior esophageal varices or liver infarction or current liver enzymes (alanine transaminase [ALT]/aspartate aminotransferase [AST]) or Total

Bilirubin >2 times the upper limit of normal (ULN), unless the patient has a diagnosis of Gilbert Syndrome.

- E 05. The patient has any clinically significant disease other than Gaucher disease, including cardiovascular, renal, hepatic, gastrointestinal, pulmonary, neurologic, endocrine, metabolic (eg, hypokalemia, hypomagnesemia), psychiatric disease, other medical conditions, or serious intercurrent illnesses that may preclude participation in the study.
- E 06. The patient is known to have any of the following: cardiac disease (congestive heart failure, recent acute myocardial infarction, bradycardia, heart block, ventricular arrhythmia), long QT syndrome, or current treatment with Class IA or Class III antiarrhythmic medicinal products.
- E 07. The patient has tested positive for the human immunodeficiency virus (HIV) antibody, hepatitis C antibody, or hepatitis B surface antigen.
- E 08. The patient has a history of cancer within 6 months of enrolment, with the exception of basal cell carcinoma.

7.2.2 Exclusion criteria related to eliglustat

- E 09. The patient is a CYP2D6 IM, EM and URM and is taking a strong or moderate CYP2D6 inhibitor concomitantly with a strong or moderate CYP3A inhibitor.
- E 10. The patient is a CYP2D6 PM having taken a strong CYP3A inhibitor within 2 weeks prior to enrolment.

7.2.3 Exclusion criteria related to the current knowledge of eliglustat

- E 11. If a female patient of childbearing potential has a positive pregnancy test blood β -Human Chorionic Gonadotropin (blood β -hCG) or is breastfeeding prior to first dosing of eliglustat in this study, the patient cannot enroll in the study at this time, but may be rescreened after the end of the pregnancy, and/or when she is no longer breast feeding, provided rescreening takes place before the end of the enrollment period.
- E 12. Women of childbearing potential who are unwilling or unable to be tested for pregnancy.

Rescreening will be allowed for patients who have failed screening because they met a temporary exclusion criterion such as concomitant medication. Patients will be allowed to rescreen only once and within 2 weeks of the 1st screening, except for pregnant or breast feeding patients who may be rescreened later, as described in E11 above.

7.3 PATIENT DISCONTINUATION/WITHDRAWAL CRITERIA

Patients are free to discontinue participation or withdraw consent from the study at any time, for any reason, and without prejudice to further treatment. Patients who discontinue/withdraw from this study will receive treatment as deemed appropriate by their treating physician.

A patient's participation in the study also may be discontinued at any time at the discretion of the Investigator or Sanofi Genzyme. The Investigator will contact Sanofi Genzyme Clinical Study Director if a patient meets any of the withdrawal criteria. The following may be justifiable reasons for the Investigator or Sanofi Genzyme to remove a patient from the study:

- The patient was erroneously included in the study.
- The patient is uncooperative, including failure to appear at one or more study visits, or is not compliant with taking study medication.
- The patient develops an exclusion criterion or concurrent disease.
- The patient receives other investigational product(s) during the course of this study.
- The patient experiences an AE that is considered intolerable by the patient or investigator.
- Sanofi Genzyme terminates the study.
- If a female patient of childbearing potential has a positive pregnancy test blood β -hCG or is lactating after first dosing with eliglustat in this study, the patient may remain in the study, but must suspend eliglustat till delivery and while breast feeding. The maximum duration of such an IMP suspension is 12 months. During the IMP suspension the patient must maintain compliance with all the other study requirements, except for the radiological examinations that are prohibited in pregnant women.

If a patient meets at least 1 of the following criteria, the Investigator must notify the Sanofi Genzyme Clinical Study Director. The Investigator and Sanofi Genzyme will review the clinical status of the patient and will determine if the patient should be withdrawn from the study.

- The patient's hemoglobin level falls below 80 g/L and remains below 80 g/L when the test is repeated within approximately 2 weeks.
- The patient's platelet count falls below 50×10^9 /L and remains below 50×10^9 /L when the test is repeated within approximately 2 weeks,
- The patient experiences a clinically significant bleeding episode assessed by the Investigator as related to a low platelet count.
- The patient experiences a decline in Gaucher disease status that, in the opinion of the Investigator, warrants discontinuation from the study (eg, repeated bone crises, clinically significant increases in liver or spleen volumes).

Patient who discontinue or withdraw from participation in the study will be contacted in order to obtain information about the reason(s) for discontinuation/withdrawal and for collection of AEs, if any. The patient will be asked to return to the clinic to complete all study discontinuation/withdrawal assessments. The Investigator will describe the reason for

discontinuation on the Completion/Discontinuation case report form. Patients who discontinue/withdraw participation from the study will not be replaced. A summary of all discontinuations will be included in the final study report.

8 STUDY TREATMENTS

8.1 INVESTIGATIONAL MEDICINAL PRODUCT

Eliglustat is supplied as 84 mg hard gelatin capsules for oral administration. Each 84 mg capsule contains 100 mg of eliglustat tartrate, which is equivalent to 84 mg of eliglustat free base.

CYP2D6 IM, EM and URM patients will receive 84 mg BID. CYP2D6 PM will receive 84 mg QD.

Given the rarity of the CYP2D6 URM phenotype, experience on treating these patients is limited. To make sure they are properly treated, additional monitoring will be performed in this patients (see [Section 10.2.3.3](#)).

Eliglustat will be taken orally with water.

For patients on BID dosing regimen, doses should be taken roughly every 12 hours (one capsule in the morning and one capsule in the evening). For patients on QD dosing regimen, doses should be taken at about the same time every day.

Eliglustat absorption is not affected by food. Therefore, it can be taken with or without food at the convenience of the patient.

8.1.1 IMP dose reduction

Certain concomitant medications require a reduction in the dose of eliglustat (see [Section 8.5.1.2](#)).

8.1.2 IMP temporary suspension

Treatment with eliglustat should be suspended in patients who require short-term treatment with

- A strong or moderate CYP2D6 inhibitor with a strong or moderate CYP3A inhibitor in CYP2D6 EMs and IMs.
- A strong or moderate CYP3A inhibitor in CYP2D6 PMs.

These medications can be used for up to 2 weeks at a time.

All IMP temporary suspension should be documented in the IMP distribution CRF.

Up to 2 episodes of eliglustat suspension are allowed per year.

If these medications are required for longer treatment periods, the investigator should consult with the Clinical Study Director.

If a patient becomes pregnant during her participation in the study she may remain in the study, but must suspend eliglustat until delivery and while breast feeding. The maximum duration of such an IMP suspension is 12 months. During the IMP suspension the patient must maintain compliance with all the other study requirements, except for the radiological examinations that are prohibited in pregnant women.

8.2 PACKAGING AND LABELING

Each bottle of IMP 84 mg capsules will contain 60 capsules and will be labeled with a single panel label. This will be provided in induction-sealed, high density polyethylene bottles with child resistant closure caps. Label text will include, at a minimum, the study protocol number, the contents of the bottle, lot number, use-by date, storage conditions and Genzyme name and address. Also included on the label will be any required cautionary statements and any other requirements, in accordance with regulations specific to each country where this study is conducted.

Packaging is in accordance with the administration schedule. The content of the labeling is in accordance with the local regulatory specifications and requirements.

8.3 STORAGE CONDITIONS AND SHELF LIFE

The IMP must be stored at a controlled room temperature of 20°C-25°C, with excursions permitted from 15°C - 30°C, in a secured location.

Investigators or other authorized persons (eg, pharmacists) are responsible for storing the IMP in a secure and safe place in accordance with local regulations, labeling specifications, policies, and procedures.

Control of IMP storage conditions, especially control of temperature (eg, controlled room temperature storage) and information on in-use stability and instructions for handling the IMP should be managed according to the rules provided by Sanofi Genzyme.

8.4 RESPONSIBILITIES

The Investigator, the hospital pharmacist, or other personnel allowed to store and dispense the IMP will be responsible for ensuring that the IMP used in the clinical trial is securely maintained as specified by the Sponsor and in accordance with applicable regulatory requirements.

All IMP will be dispensed in accordance with the Investigator's prescription and it is the Investigator's responsibility to ensure that an accurate record of IMP issued and returned is maintained.

Any quality issue noticed with the receipt or use of an IMP (deficiency in condition, appearance, pertaining documentation, labeling, expiration date, etc.) should be promptly notified to Genzyme. Some deficiencies may be recorded through a complaint procedure.

A potential defect in the quality of IMP may be subject to initiation of a recall procedure by Genzyme. In this case, the Investigator will be responsible for promptly addressing any request made by Genzyme, in order to recall IMP and eliminate potential hazards.

Under no circumstances will the Investigator supply IMP to a third party, allow the IMP to be used other than as directed by this clinical trial protocol, or dispose of IMP in any other manner.

8.4.1 Treatment accountability and compliance

At each visit the Investigator or his/her delegate will question patients to assess treatment compliance and will remind patient of the importance of excellent treatment compliance.

IMP accountability:

- Treatment units are returned by the patient at each visit;
- The Investigator or delegate records the dosing information on the appropriate page(s) of the CRF;
- The monitor in charge of the study then checks the CRF data by comparing them with the IMP that he/she has retrieved and the treatment log forms.

8.4.2 Return and/or destruction of treatments

All used, partially-used or unused treatment bottles will be retrieved from each patient at each site visit. A detailed treatment log of the patient returned bottles (used, partially used, or unused) to the site will be established. Any IMP destroyed on site or returned to Genzyme will be documented in the treatment log and associated Sponsor form(s). The Investigator will not destroy any IMP unless Genzyme provides written authorization. Please refer to the study Pharmacy Manual for further details.

8.5 CONCOMITANT MEDICATION

Patients will be monitored continuously for changes in the use of concomitant medications (introduction of new medications and changes in the dose or regimen of preexisting medications).

Patients will be instructed to report to the Investigator any changes in concomitant medications before these changes are made, or, in the case of changes made in emergency situations, as soon as possible.

8.5.1 INTERACTION WITH OTHER MEDICINAL PRODUCTS AND OTHER FORMS OF INTERACTION**8.5.1.1 ANTIARRHYTHMICS**

Because eliglustat is predicted to cause mild increases in ECG intervals (PR, QTc, and QRS) at substantially elevated eliglustat plasma concentrations, use of eliglustat is prohibited in combination with Class IA and Class III antiarrhythmic medications. Patients who require long term treatment with any of these medications should be removed from the study.

8.5.1.2 EFFECT OF OTHER DRUGS ON ELIGLUSTAT

Eliglustat is metabolized primarily by CYP2D6 and to a lesser extent by CYP3A4. Concomitant administration of substances affecting CYP2D6 or CYP3A4 activity (ie, CYP2D6/CYP3A inhibitors and CYP3A strong inducer) may alter Genz-99067 plasma concentrations. Grapefruit products contain one or more components that inhibit CYP3A and can increase plasma concentrations of eliglustat. Grapefruit and grapefruit products including grapefruit juice, but not grapefruit seeds, are prohibited at any time during the study.

Table 1 provides an overview of allowed and prohibited inhibitors and inducers for chronic use, as determined by the patient's CYP2D6 phenotype.

Table 1 - Concomitant Medications Recommendations for Use with Eliglustat

CYP2D6 Phenotype	Category of Inducer / Inhibitor						
	Strong CYP3A Inducer	Weak CYP3A Inhibitor ALONE	Moderate CYP3A Inhibitor ALONE	Strong CYP3A Inhibitor ALONE	Moderate CYP2D6 Inhibitor ALONE	Strong CYP2D6 Inhibitor ALONE	Moderate or Strong CYP3A Inhibitor and Moderate or Strong CYP2D6 Inhibitor COMBINED
Poor Metabolizer	Not recommended	Use with caution	Not recommended	Contraindicated	Allowed	Allowed	Moderate CYP3A Inhibitor and Moderate or Strong CYP2D6 Inhibitor COMBINED As moderate CYP3A inhibitor alone (Not recommended)
Intermediate and Extensive Metabolizer	Not recommended	Allowed at usual dose of 84 mg BID	Use with caution	Use with caution	Use with caution	84 mg once daily	Contraindicated
Ultra-Rapid Metabolizer	Not recommended	Allowed	Allowed	Allowed	84 mg once daily	84 mg once daily	Contraindicated

8.5.1.3 EFFECT OF ELIGLUSTAT ON OTHER DRUGS

In vivo eliglustat was found to be an inhibitor of P-glycoprotein (P-gp; 1.5-fold increase in digoxin area under the plasma concentration versus time curve from 0 to the real time corresponding to the last concentration above the lower limit of quantification) and an inhibitor of CYP2D6 (2.1-fold in metoprolol area under the plasma concentration versus time curve extrapolated to infinity [area under the concentration-time curve (AUC)]), consistent with in vitro data showing eliglustat to be an inhibitor of CYP2D6 and of P-gp. Eliglustat may increase the plasma concentration of those substances and should be used with caution in combination with a P-gp or a CYP2D6 substrate. Lower doses of such drugs may be required.

9 ASSESSMENT OF INVESTIGATIONAL MEDICINAL PRODUCT

9.1 PRIMARY ENDPOINT

The main purpose of this extended treatment study is to evaluate long term skeletal responses to eliglustat after 2 additional years of treatment with eliglustat. Five common skeletal manifestations of Gaucher disease will be assessed:

1) Mobility, bone pain and bone crisis, as assessed by the Gaucher Disease clinical assessments; 2) bone marrow infiltration; 3) BMD; 4) Lytic lesions, osteonecrosis, fractures and infarcts; 5) bone biomarkers

9.1.1 Gaucher disease clinical assessments (mobility, bone pain, bone crisis).

Patients will be asked to rate

- Current mobility
 - Unrestricted mobility
 - Walks with difficulty
 - Walks with orthopedic aid
 - Requires wheelchair
 - Bedridden
- Level of bone pain during the last 4 weeks as
 - None
 - Very mild
 - Mild
 - Moderate
 - Severe
 - Extreme
- In addition, investigators will report the number of bone crisis since the previous assessment. Bone crisis is defined as pain with acute onset, which requires immobilization of the affected area, narcotics for relief of pain, and may be accompanied by one or more of the following: periosteal elevation, elevated white blood cell count, fever, or debilitation of >3 days.

Gaucher disease clinical assessments will be performed at screening and then yearly.

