10.2.1 Screening period

Screening will be performed between 45 and 1 day before Day 1 of the study. Screening can be performed at the time of the EOS visit of the previous study the patient was enrolled in.

Final GZGD00304, GZGD02507, GZGD02607 and GZGD03109 study assessments may serve as entry evaluation for this study if performed less than 3 month for laboratory testing, 1 year for bone imaging and 6 months for other assessments.

However, safety (S)AE, concomitant medication and prior medication history, physical examinations, HIV antibody, hepatitis C antibody, or hepatitis B surface antigen, blood pregnancy test, height will have to be performed in all cases.

Patients will be assigned a unique ID number. This new ID number as well as the number of the previous study the patient was enrolled in and his/her ID number in that study will appear in the clinical database.

For some assessments it will be possible to use results from the end of study visit of the previous eliglustat study the patient was enrolled in. For others they will need to be performed anew. See detail below.

The screening procedures do not have to be performed over 2 visits. Scheduling will be based on investigator, patient and resources availability.

After completion of all the screening assessments, the investigator will review their results to confirm that each patient meets all the inclusion criteria and none of the exclusion criteria before scheduling the patient for the Day 1 visit.

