10.2.1.1 Clinical information

- Demographic data will be entered in the corresponding CRF.
- Previous medical/surgical history entered in the CRF of the previous study should not be re-entered in the Medical history CRF of this study, but will be used in the analysis of this study.
- The following categories of medico/surgical events are considered part of the medical/surgical history of the patient and should be entered in the Medical/surgical history CRF:
 - AEs started during the previous study, which are closed at the time of the screening visit and are still considered clinically significant by the investigator at the time of the screening visit.
 - Medical/surgical events started after the follow-up phone call of the previous study and before the ICF signing in the current study, whether ongoing or closed, if they are considered clinically significant by the investigator.
 - Clinically significant abnormal laboratory test results at Visits 1 and 2 (Screening period)
- AEs started during the previous study, which are ongoing at the time of the screening visit should be entered in the AE CRF regardless of whether the patient had a gap in eliglustat treatment after the end of the previous study, or the end of study visit of the previous study and the screening visit of this study are concomitant.
- Concomitant medications: Any concomitant medication the patient is taking at the time of screening or took during the previous 30 days. This should include eliglustat if the last dose of eliglustat in the previous study was taken 30 days or less prior to the screening

visit. ERT should be included if the patient was on ERT during the period between the end of the previous study and the screening visit.

- Complete physical exam including weight and height
- Gaucher disease clinical assessments
- SF-36, to be completed at the study site by the patient before any other study assessment.

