##### **2.4.4.1.1 Mobility, bone pain and bone crisis**

Category of mobility status and bone pain, as well as number of new bone crises, will be summarized by visit. Absolute value, change from baseline and percent change from baseline of bone crisis over time will be summarized using descriptive statistics by visit using two baselines (study baseline and eliglustat baseline). Additionally, shifts in category of mobility and pain from study and eliglustat baseline by each post-baseline visit will be presented.

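### The first on-study bone-crisis count starts before Day 1, and its change from baseline compares look-back periods that nothing makes equal

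*Protocol*

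**What the plan says.** Bone crisis belongs to the first of five primary skeletal domains, which are summarised separately and descriptively (protocol 9.1 and 11.4.2.1). Protocol 9.1.1, repeated in SAP 2.1.3.1.1, defines what is recorded: "In addition, investigators will report the number of bone crisis since the previous assessment". On timing it adds: "Gaucher disease clinical assessments will be performed at screening and then yearly". Bone pain, in the same section, has a fixed 4-week recall; bone crisis has no fixed period. The SAP's count categories (none, 1 to 2, more than 2) carry no time unit either.

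On the entry assessment, protocol 10.2.1 states: "Screening will be performed between 45 and 1 day before Day 1 of the study". It also lets a final assessment from the earlier study stand in, with age limits of "1 year for bone imaging and 6 months for other assessments". The list of items that must be redone regardless ends with "blood pregnancy test, height will have to be performed in all cases", and the Gaucher disease clinical assessments are not on it. The Day 1 visit (protocol 10.2.2 and flow chart 1.2) contains no Gaucher assessment.

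Protocol 10.2.1.1 foresees that treatment between studies may differ. Ongoing adverse events are entered "regardless of whether the patient had a gap in eliglustat treatment after the end of the previous study", and for prior medication "ERT should be included if the patient was on ERT during the period between the end of the previous study".

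For analysis, SAP 2.4.4.1.1 says: "Absolute value, change from baseline and percent change from baseline of bone crisis over time will be summarized". This is done by visit, against both the study baseline and the eliglustat baseline.

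**The concern.** A count that runs back to the last assessment depends on how far away that assessment was. Here the start of the first on-study interval is set by when the baseline assessment happened, not by the first dose in this study. Crises from before Day 1, possibly from time off eliglustat or on ERT, can therefore be tabulated as on-study events.

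Subtracting one such count from another adds a second problem. If the two intervals differ in length, the change from baseline partly measures visit spacing. The descriptive summaries are the study's whole primary result, so no test or model downstream would correct this.

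**Working it through.** The plan gives no figure to reproduce: there is no crisis rate, no sample size calculation and no hypothesis test. The check is look-back arithmetic.

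**Step 1: the Week 52 look-back.** Inputs are the Week 52 target day of 364 (SAP Table 2), screening at Day -45 to -1, and a carry-over limit of 6 months, taken as 26 × 7 = 182 days. I use the yearly schedule of protocol 9.1.1, the flow chart and SAP Table 1; protocol section 4 says twice-yearly, which conflicts with these.

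Look-back = 364 + days from baseline assessment to Day 1. Share before Day 1 = those days ÷ look-back.

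| Baseline assessment | Days before Day 1 | Look-back | Share before Day 1 | Ratio to 364 |
|---|---|---|---|---|
| Fresh, Day -1 | 1 | 365 | 1/365 = 0.3% | 1.00 |
| Fresh, Day -45 | 45 | 409 | 45/409 = 11.0% | 1.12 |
| Carried over, 26 weeks old at Day 1 | 182 | 546 | 182/546 = 33.3% | 1.50 |

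The protocol does not say whether the 6 months are counted at screening or at Day 1. If counted at a Day -45 screening, the last row becomes 182 + 45 = 227 days and a look-back of 364 + 227 = 591. The Week 104 count covers about 364 days in every case, so with carry-over the two on-study counts also differ in length.

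**Step 2: the baseline look-back.** There are two cases.
- Assessment carried over, or done at the end-of-study visit of the earlier study: the count covers the last inter-visit interval of that study. Its length is not in the documents.
- Assessment done anew later: the count covers the gap since the final visit of the earlier study. Nothing fixes its length.

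**Step 3: expected change at a constant rate r.** Expected count = r × look-back, so expected change = r × (on-study look-back − baseline look-back). It is zero only when the two are equal. The ratio of expected counts does not depend on r. Baseline look-backs of 3, 6 or 12 months are my assumption, to show the range:

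| Assumed baseline look-back | On-study 364 days | On-study 546 days |
|---|---|---|
| 91 days | 364/91 = 4 (+300%) | 546/91 = 6 (+500%) |
| 182 days | 364/182 = 2 (+100%) | 546/182 = 3 (+200%) |
| 364 days | 364/364 = 1 (0%) | 546/364 = 1.5 (+50%) |

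Treating 364 days as one year, the absolute changes are 0.75r, 0.5r and 0 in the first column, and 1.25r, 1.0r and 0.5r in the second. With an assumed r of 0.02 per patient-year they run from 0 to 0.025 crises per patient; with 0.2, from 0 to 0.25. These illustrate the mechanism and are not estimates. For an individual patient, percent change is also undefined whenever the baseline count is zero.

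**The case against.** **Carry-over is optional.** With fresh screening at most 11% of the Week 52 interval precedes Day 1, and the 546-day figure is a near-maximum. The documents do not say how many patients it would affect. This stands, and it limits the size.

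**Long gaps mostly fall elsewhere.** An assessment 6 months old or more must be redone, so a long gap between studies goes into the baseline count and only 1 to 45 days reach Week 52. This also stands. A reader might infer that the Week 52 count does contain off-treatment crises. The documents support only that it can: the interval always includes time before Day 1, but a crisis need not occur in it, and screening may coincide with the earlier study's last visit, leaving little or no gap.

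**Incidence rates are already foreseen.** The protocol synopsis, protocol 11.4 and SAP 2.4.4 mention them in general terms, where appropriate. But SAP Appendix B gives an annual rate only to the imaging events and enters No for the clinical assessments. Nor would a rate alone be enough. Pre-Day-1 crises divided by person-time from Day 1 would, in the 6-month case at a constant crisis rate, inflate the rate by 546/364 = 1.50 at one year and (728 + 182)/728 = 1.25 at two.

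**Crises may be dated elsewhere.** Adverse events are recorded from consent with onset dates (protocol 10.5.2), and patients are contacted about every 4 weeks. This makes the fix cheaper, but no text links those dates to the bone-crisis count.

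**The SAP limits which baselines are used.** The eliglustat baseline applies only where assessments are comparable (SAP 2.4), and the Schedule B baseline window of [-45, 1] would exclude an older carried-over value. That window conflicts with protocol 10.2.1 and with the last-non-missing-value rule in SAP 2.4. It could remove a baseline value, but it does not shorten the Week 52 look-back.

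**Impact is limited.** Bone crisis is one item in one of five domains, with no composite, test or decision rule. True.

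**Conclusion.** The point holds as a defect in how one descriptive item of the primary endpoint is counted and compared. The Week 52 look-back always starts before Day 1: by 1 to 45 days with fresh screening, or by up to about 6 months with carry-over (age counted at Day 1). The first on-study count can therefore include pre-Day-1 crises, possibly off eliglustat. Change and percent change of the raw count compare intervals that nothing in the plan makes equal.

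The look-back figures follow from the documents. The size of the artificial change does not, because the crisis rate and the earlier studies' look-back are not given. A reader might infer that the change is never zero, or that it runs in a known direction. Neither is supported. It is zero when the look-backs match, positive when the on-study interval is longer, and negative when the baseline interval is longer, for example after fresh screening more than about a year after the earlier study's final visit. The documents do not say which of these patients will present. No test, sample size or other domain is affected.

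**What to change.** - **Protocol 9.1.1 and SAP 2.1.3.1.1:** count as on-study only crises with onset on or after Day 1. Any of three sources would do: a crisis onset date on the CRF, the adverse-event onset dates already collected (if every crisis is reported as an adverse event), or one question at the existing Day 1 visit to close the earlier interval.
- **Reporting:** show crises between the baseline assessment and Day 1 separately.
- **SAP 2.4.4.1.1 and Appendix B:** replace change and percent change of the raw count with crises per patient-year from Day 1, using the events-over-person-years calculation that SAP 2.4.4.1.4 already specifies for imaging events. Set a pre-study rate beside it only where the length of its look-back is known.

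The cost is one CRF field or one question, plus SAP wording. The downside is that no pre-study rate can be shown for patients whose look-back is unknown.
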